1 STUDY OBJECTIVES AND ENDPOINTS

1.1 Objective

The objective is to determine the optimum dose of thrombolytic and duration of the ultrasound procedure (together defined as the APT Procedure) as a treatment for acute submassive PE. Symptomatic submassive PE are patients with acute (≤ 14 days) PE with normal systemic arterial blood pressure (>90 mmHg) and evidence of RV dysfunction (Right Ventricular to Left Ventricular diameter ratio, i.e., RV/LV ratio ≥ 0.9).

1.2 Primary Efficacy Endpoint

The primary efficacy endpoint is the change in the ratio of the measurement of the RV/LV as measured by computed tomographic angiography (CTA) from baseline to 48 ± 6 hours after the start of the APT Procedure.

1.3 Secondary Efficacy Endpoints

1. Change from Screening/Baseline in echocardiographic parameters including RV/LV ratio, Tricuspid Annular Plane Systolic Excursion (TAPSE), estimated Right Ventricular Systolic Pressure (RVSP), and collapse of the inferior vena cava (IVC) with respiration within 4 hours after the end of the APT Procedure, 24 and 48 hours after the start of the APT Procedure, and at 30 days, 90 days and 365 days after the end of the APT Procedure.
2. Change from Screening/Baseline in thrombus burden by modified Miller score as assessed by CTA at 48 hrs. after the start of the APT Procedure.
3. Freedom from major harm occurring between enrolment and 30 days and assessed by the Safety Monitor using the following criteria:
 - a. Mortality – all cause and PE related
 - b. CV collapse: Defined as one or more of the following:
 - i. >40 mmHg drop in SBP (for >15 minutes from documented blood pressure as an in-patient) despite IV fluid challenge and absence of new atrial arrhythmia.
 - ii. Requirement for emergency systemic thrombolysis
 - iii. Requirement for emergency surgical embolectomy
 - iv. Requirement for vasopressors
 - v. Intubation/Ventilation
 - c. Major bleeding per ISTH
 - d. Recurrent PE (confirmed by imaging)
 - e. Surgical correction of device related complication
4. Change over time in 6 minute walk (6MW) distance with BORG score and requirement for oxygen therapy at all post-hospitalization subject visits

5. Change in Quality of life (QOL) as measured by the Pulmonary Embolism Quality of Life (PEmb-QOL) and EuroQual - 5 Dimensions – 5 Levels (EQ-5D-5L) at all post-hospitalization subject visits and phone contacts.
6. Healthcare resource utilisation during hospitalisation:
 - a. Time from hospital admission to diagnosis of PE
 - b. Time from diagnostic CT scan to initiation of treatment for PE
 - c. Time in each Level of Care (Level 0 and 1; Level 2; and/or Level 3) through discharge. Levels are defined according to National Framework Document.
 - d. Team managing the pt – specialties involved
7. Healthcare resource utilisation after hospitalisation and during 12 month follow-up:
 - a. Team managing the pt - specialties
 - b. HCP visits for VTE
 - c. Hospital re-admission frequency and duration

1.4 Safety Endpoints

1.4.1 Primary Safety Outcome

The primary safety outcome is frequency of major bleeding within 72 hours after initiating the APT Procedure. Evaluation of clinically overt bleeding will depend upon the suspected bleeding site and clinician's judgment. Major bleeding events will be defined according to the International Society on Thrombosis and Haemostasis (ISTH) criteria for major bleeding as assessed by the Medical Monitor

1. Fatal bleeding and/or
2. Symptomatic bleeding in a critical area or organ (intracranial, intraspinal, intraocular, retroperitoneal, intra-articular or pericardial, or intramuscular with compartment syndrome) and/or
3. Bleeding causing a fall in hemoglobin level of 20 g/L or more, or leading to transfusion of two or more units of whole blood or red blood cells

1.4.2 Secondary Safety Outcomes

1.4.2.1 *Technical procedural complications*

Technical complications associated with the use of the EkoSonic® device will be recorded during catheter placement in the pulmonary artery and during the infusion procedure. Any significant dissection or perforation of the pulmonary arteries will be visible on the follow-up CTA.

1.4.2.2 Symptomatic recurrent PE

For the diagnosis of symptomatic recurrent PE throughout the study, documentation of clinical symptoms and/or signs suggesting recurrent PE is required in combination with objective confirmation with CTA, ventilation-perfusion lung scanning, or invasive contrast PAgram. Specifically, symptomatic recurrent PE will be diagnosed if a new filling defect (compared with the baseline CTA) is demonstrated on CTA or invasive contrast PAgram.

1.4.2.3 Mortality

All-cause mortality throughout the study will be recorded. Cause of death will be classified as related to cancer, myocardial infarction, PE, or other disease state based on MedDRA preferred terms for SAE with outcome of death.

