3.4.2.3 Mortality

All-cause mortality throughout the study will be recorded. Cause of death will be classified as related to cancer, myocardial infarction, PE, or other disease state. Death will be attributed to PE if it is either unexplained or sudden or if there is evidence to support an association with PE.

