8.12 Expedited Reporting Of Serious Adverse Events

Any AE that is considered serious must be reported to the device manufacturer, EKOS Corporation, within 24 hours of the site's knowledge of the event throughout the study. The Investigator will enter into EDC as much of the information listed below is available within 24 hours. An automatically generated email notification will be sent to EKOS when the event is classified as a Serious Adverse Event in EDC.

- a. Subjects demographics
- b. Pre-existing conditions
- c. The adverse event's description
- d. Date and time of AE onset
- e. Severity
- f. Treatment
- g. Results of diagnostic testing
- h. Duration of sequelae
- i. Outcome (if known)
- j. Information on suspected medications

When a device-related SAE is reported, the device must be retained and returned to EKOS (see above for address for return devices). The EKOS representative may contact the Investigator to collect additional information on EKOS.

When reporting a death, the primary event or condition that caused or contributed to the fatal outcome will be reported as the serious adverse event. Death would be reported as the outcome of the serious adverse event. If the cause of death is unknown at the time of reporting, record “unknown cause of death.”

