8.13 Safety Monitor

A safety monitor will review all AEs, adjudicate all SAEs and major bleeding events during the study, as well as assess freedom from major harm occurring between enrolment and 30 days for each subject. The safety monitor will determine if the AE meets the definition of serious and unexpected and will notify EKOS if the number or type of events is of concern.

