2.3.2 Secondary Efficacy Analyses

Secondary efficacy outcomes are the following:

1. Change from baseline in echocardiographic parameters including RV/LV ratio, TAPSE, estimated RVSP, and collapse of the IVC with respiration within 4 hours of the end of the APT procedure,

24 and 48 hours after start of the APT procedure, 30 days, 90 days and 365 days after the APT procedure (procedure start date = Day 0)

2. Change from baseline in thrombus burden by modified Miller score as assessed by CTA at 48 hours after the start of the APT procedure
3. Freedom from major harm occurring between enrolment and 30 days and assessed by the Safety Monitor using the following criteria:
 - a. Mortality – all cause and PE related
 - b. CV collapse: Defined as one or more of the following:
 - i. >40mmHg drop in SBP (for >15 minutes from documented blood pressure as an in-patient) despite IV fluid challenge and absence of new atrial arrhythmia.
 - ii. Requirement for emergency systemic thrombolysis
 - iii. Requirement for emergency surgical embolectomy
 - iv. Requirement for vasopressors
 - v. Intubation/Ventilation
 - c. Major bleeding per ISTH
 - d. Recurrent PE (confirmed by imaging)
 - e. Surgical correction of device related complication
4. 6 minute walk (6MW) distance with BORG score and requirement for oxygen therapy at 30 days, 90 days and 365 days, and changes from 30 days
5. Quality of life (QOL) as measured by the Pulmonary Embolism Quality of Life (PEmb-QOL) and EuroQual - 5 Dimensions – 5 Levels (EQ-5D-5L) at all post-hospitalization subject visits and phone contacts.
6. Healthcare resource utilisation during hospitalisation:
 - a. Time from hospital admission to diagnosis of PE
 - b. Time from diagnostic CT scan to initiation of treatment for PE
 - c. Time in each Level of Care (Level 0 and 1; Level 2; and/or Level 3) through discharge. Levels are defined according to National Framework Document.
 - d. Team managing the pt – specialties involved
7. Healthcare resource utilisation after hospitalisation and during first 12 months:
 - a. Team managing the pt - specialties
 - b. HCP visits for VTE
 - c. Hospital re-admission frequency and duration

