2.4 Safety Analysis

Safety analyses will be performed for the **Safety Subject Set**.

For the primary safety analysis, the number and percentage of subjects with major bleeding events within 72 hours of start of APT procedure will be reported with a 95% Wilson confidence interval.

Secondarily, the frequencies and proportions of subjects with technical procedural complications, symptomatic recurrent PE, and all cause mortality through the 365 day follow-up period will be reported with 95% Wilson score confidence intervals.

In addition, adverse events experienced through 30 days and SAEs through 365 days will be mapped to standard terms and summarized. For a given event, the frequency and proportion of subjects reporting it will be tabulated according to the worst severity experienced. Two separate tables will be constructed for each a) all reported events, b) events related to interventional procedure (not EKOS system), c) events related to EKOS system, d) events related to thrombolytic drug, e) events related to anticoagulant drug, f) bleeding events (3rd table will be constructed through 72 hours), and g) SAEs.

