At select participating sites: In addition to the vital signs specified in Section 7.4, bedside vital signs including, systolic/diastolic blood pressure, heart rate, respiratory rate, capillary refill time and SpO2 will be recorded at the start of the APT Procedure, and at each 30 minute interval until 4 hours post-completion of the APT Procedure. Along with the echocardiograms specified in Section 7.7, limited echocardiograms performed at the bedside for RV/LV ratio measurements will be obtained hourly after the start of the APT Procedure through 4 hours post procedure.

Scatterplots of RV/LV ratio (y-axis) vs vital sign measures (x-axis) and of change in RV/LV ratio vs changes in vital sign measures will be presented to assess the correlation of change in clinical parameters (vital signs) with change in markers of RV strain (RV/LV ratio), and associated Pearson or Spearman correlation coefficients, where applicable.

Subject Set = Safety Subject Set for (19 – 23)

- 21) Major Bleeding Events within 72 hours of initiation of APT*
- 22) Technical Procedural Complications (*captured on the EkoSonic Device CRF as “Was this device successfully placed and used for treatment?”; make this a by-patient listing*)
- 23) Symptomatic Recurrent PE and Symptomatic Recurrent PE up to Day 365 (Confirmed by imaging)
- 24) All cause mortality up to Day 30 and all cause mortality up to Day 365 (*note: per AE and study exit CRFs*)
- 25) Adverse Events (*Run tables for AEs up to Day 30: AE start date ≤ Date of 30 Day Follow Up Visit per Follow-Up CRF*)
 - a) All reported events
 - b) Related to interventional procedure (not EKOS system)
 - c) Related to EKOS system
 - d) Related to thrombolytic drug
 - e) Related to anticoagulant drug
 - f) Bleeding events (*all site reported bleeding events, make tables for:*
-All reported bleeding events
-Those within 72 hours of APT start
-Those related to:
-interventional procedure (not EKOS system)
-EKOS system
-thrombolytic drug
-anticoagulant drug
 - g) SAEs

Also run analyses for (g) through Day 365, including those through 30 days.

26) Freedom from major harm occurring between enrolment and 30 days and assessed by the Safety Monitor using the following criteria:

- a. Mortality – all cause and PE related
- b. CV collapse: Defined as one or more of the following:
 - i. >40mmHg drop in SBP (for >15 minutes from documented blood pressure as an in-patient) despite IV fluid challenge and absence of new atrial arrhythmia.

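### The SAP classifies cause of death from MedDRA preferred terms and omits the protocol's rule for attributing death to PE, so the two documents can class the same death differently

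*SAP*

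**What the plan says.** Protocol 3.4.2.3 and SAP 1.4.2.3 both list mortality as a secondary safety outcome and sort deaths into cancer, myocardial infarction, PE or other disease. They differ on how a death gets its category.

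- Protocol 3.4.2.3: "Death will be attributed to PE if it is either unexplained or sudden or if there is evidence to support an association with PE".
- SAP 1.4.2.3: the category is assigned "based on MedDRA preferred terms for SAE with outcome of death". It has no default for an unexplained or sudden death, and it neither mentions the protocol rule nor explains the change.

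Three other places matter.

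- Protocol 8.12 tells sites what to enter "If the cause of death is unknown at the time of reporting": the cause is recorded as unknown.
- Protocol 8.13 has the Safety Monitor "adjudicate all SAEs and major bleeding events during the study" and assess 30-day major harm for each subject.
- SAP 2.3.2 defines the endpoint "Freedom from major harm occurring between enrolment and 30 days and assessed by the Safety Monitor using the following criteria". Its first criterion, repeated in Appendix 1 item 26a, is mortality, both all-cause and PE-related.

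**The concern.** Two governing documents give different rules for the same safety classification, and they disagree on a kind of death that the protocol itself foresees. The protocol resolves uncertainty toward PE. The SAP relies on the coded term, which for a death of unknown cause need not name PE. The protocol's further criterion, evidence of an association with PE, is a judgement that a preferred term reflects only if the site reported PE as the fatal event.

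What is at stake is the count of PE-related deaths in the cause-of-death classification and, if shown separately, in the PE-related part of major harm. The SAP does not say which rule the Safety Monitor should use for that part. One death could therefore be PE-related in one output and other disease in another. In a PE treatment trial this is the cause category readers will look at first.

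**Working it through.** The plan gives no figure for PE-related mortality, so there is none to reproduce. The check compares the texts and then illustrates the scale.

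**Step 1. Follow each type of death through both rules.**

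| Death | Protocol 3.4.2.3 | SAP 1.4.2.3 |
|---|---|---|
| Fatal SAE reported and coded as PE | PE | PE |
| Cause stays unknown; coded as unknown | PE | Not PE (no PE term) |
| Coded only as sudden death | PE | Not PE (no PE term) |
| Cause first unknown, later diagnosed and updated | Follows the diagnosis, unless the death was sudden | Follows the updated term |
| Clear non-PE cause, neither sudden nor unexplained, no evidence of PE | Not PE | Not PE |

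The rules part in rows 2 and 3, and in row 4 for a sudden death updated to a non-PE term.

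**Step 2. Direction.** A death coded to a PE term would also meet the protocol's evidence criterion. The deaths classed as PE under the SAP are therefore a subset of those classed as PE under the protocol. Omitting the rule can lower the PE count and cannot raise it.

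**Step 3. Which planned results use cause of death.**

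- SAP 2.4: "all cause mortality through the 365 day follow-up period will be reported with 95% Wilson score confidence intervals". Cause plays no part.
- SAP Appendix 1 item 24: "All cause mortality up to Day 30 and all cause mortality up to Day 365". Again all-cause.
- Protocol 10.4: death over 365 days, also without regard to cause.
- Freedom from major harm: every death to 30 days is already a failure under the all-cause criterion, so the composite is the same under either rule.

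That leaves the descriptive cause classification and the PE-related part of criterion (a).

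**Step 4. Scale of one death.** The SAP synopsis gives n = 29 for the UK extension. Assumptions: all 29 are in the Safety Subject Set, and x deaths remain coded as unknown or sudden. The interval is the SAP's own Wilson method with z = 1.96, so z² = 3.84 and n + z² = 32.84:

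(x + z²/2 ± z·√(x(n − x)/n + z²/4)) / (n + z²)

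- SAP rule, x = 0 counted: lower limit 0; upper limit 3.84/32.84 = 11.7%.
- Protocol rule, x = 1 counted: 1/29 = 3.4%. Centre (1 + 1.92)/32.84 = 8.9%. Half-width 1.96 × √(28/29 + 0.96)/32.84 = 1.96 × 1.388/32.84 = 8.3%. Interval 0.6 to 17.2%.
- Protocol rule, x = 2 counted: 2/29 = 6.9%, interval 1.9 to 22.0%.
- No such death: 0/29 under both rules.

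**The case against.** The strongest reply is that almost no planned result moves. The analysed mortality rates are all-cause, no listed table reports PE mortality on its own, and the composite counts every death. The one endpoint that names PE-related death is assessed by the Safety Monitor, and SAP 1.4.2.3 does not say that its rule governs that assessment. All of this stands and limits the point to a classification.

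A reader might infer that PE mortality is undercounted. The documents do not support that. They report no UK deaths, and the protocol rule is an inclusive default that may itself count too many deaths as PE over a year of follow-up. They show only that the two rules can differ, and in which direction.

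A reader might also expect a PE death reported as, say, cardiac arrest to be lost. The reporting rules point the other way. Protocol 8.12 asks for the primary event that caused or contributed to death, and Protocol 8.9 asks for the diagnosis and for the causative event in a cascade. Losing such a death would require misreporting. Protocol 8.9 also has later diagnoses reported as follow-up, so an entry of unknown cause may be temporary.

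Finally, a shift of 10 percentage points in an arm of about 10 is an easy figure to quote, but the documents give no UK enrolment by arm.

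None of this removes the conflict for a death that stays unexplained or is coded only as sudden.

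**Conclusion.** The point holds as an inconsistency of limited reach that should be corrected. SAP 1.4.2.3 replaces the protocol's attribution rule with a coding rule, without saying so, and a death left coded as unknown or sudden is then PE-related in one document and not in the other. Any shift is toward fewer PE deaths. On the stated assumptions, one such death is the difference between 0/29 and 1/29 (3.4%). With none, that default makes no difference. All-cause mortality and the major-harm composite are unaffected in every case. It would go too far to say that the SAP knowingly overrides the protocol, since it is silent on the protocol rule.

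**What to change.** In SAP 1.4.2.3, restore the attribution rule of Protocol 3.4.2.3. State that the Safety Monitor applies it during the existing adjudication of SAEs and records one cause category for each death. Use that same classification for the PE-related part of major harm in Appendix 1 item 26a. Keep MedDRA preferred terms for adverse event tabulation only.

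The cost is small: a short SAP revision and one recorded category per death. It is not quite wording alone, because Protocol 8.13 covers adjudication of SAEs but does not explicitly mention cause of death, so that field may have to be added to the adjudication record. No further data from subjects appear to be needed.

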2 STATISTICAL ANALYSIS

2.1 Analysis Subject Sets and Missing Data Handling Convention

The **Intent-to-Treat (ITT) Subject Set** includes all randomized subjects; analyses will be performed for all primary and secondary efficacy endpoints for the ITT Subject Set. Unless otherwise specified, all available data will be used for ITT analyses regardless of whether the assessment timing is within the specified window.

The **Efficacy Evaluable (EE) Subject Set** includes randomized subjects who received the APT Procedure with EKOS treatment and for whom a CTA calculated RV/LV ratio is available at both baseline and 48 ± 6 hours from the beginning of the APT procedure. For the primary endpoint of CTA RV/LV ratio change from baseline to 48 ± 6 hours only, a subset analysis will be performed for EE patients in the ITT Subject Set. These analyses will only include data obtained in the pre-specified windows of (a) within 48 hours before APT start for baseline and (b) within ± 6 hours for 48 hours from APT start.

Safety Evaluable Subjects are defined as enrolled subjects for whom the APT Procedure was initiated, i.e. venous access attempted for EkoSonic catheter introduction, as indicated in database by a non-mising start time for EkoSonic placement (EXSTTM in the interventional procedure (EX) dataset). The **Safety Subject Set (SSS)** includes all safety evaluable subjects and will be used for all safety analyses.

Missing data will not be imputed for the efficacy and safety analyses.

